2.5.2 Statistical hypothesis, model, and method of analysis

Analysis of above secondary efficacy endpoints will be based on FAS (Core Period) or RTS (Retreatment Period), except the following endpoints:

- Proportion of participants meeting criteria for relapse over fixed period in the Extension Period will be based on ENS
- Proportion of relapsing participants meeting response criteria or remission criteria after the first infusion of MIJ821 retreatment in the Extension Period will be based on RTS

No hypothesis will be tested for the secondary efficacy endpoints.

Frequency tables (count and proportion) will be provided for these endpoints by analysis visit after imputation for missing values. Details on missing data handling are described in [Section 2.5.1](#). Bar chart will be plotted by treatment arm and analysis visit.

The proportion of participants meeting criteria for relapse over 1 month, 2 months, 3 months, 6 months 9 months and 12 months in Extension Period will be plotted for each treatment arm based on ENS for responders/remitters at EoC visit. In addition for responders/remitters, the time to first relapse will be analyzed by kaplan-meier (KM) method and display in KM plots. The median time to first relapse will be summarized with 90% CI.

If data warranted, the treatment differences of each MIJ821 dose versus Placebo will be analyzed separately, using a repeated logistic regression model, for following endpoints:

- Proportion of participants meeting response criteria ($\geq 50\%$ reduction from baseline in MADRS total score) over time in the Core Period.
- Proportion of participants meeting criteria for sustained response ($\geq 50\%$ reduction from baseline in MADRS total score sustained for a period of at least four weeks) in the Core Period
- Proportion of participants meeting remission criteria (MADRS total score of ≤ 12) over time in Core Period
- Proportion of participants meeting criteria for sustained remission (MADRS total score of ≤ 12 sustained for a period of at least four weeks) in the Core Period

For response rate and remission rate per visit, the repeated logistic regression model will be established with the fixed, categorical effects of treatment (6 dose arms and 1 placebo arm), time, treatment*time interaction, region, the fixed continuous baseline MADRS score, and baseline score*time interaction. [REDACTED]

[REDACTED]

For sustained reponse rate and remission rate, the logistic regression model with firth method will be fitted, involving fixed, categorical effects of treatment (6 dose arms and 1 placebo arm), region, and the fixed continuous baseline MADRS score. The estimated arm-level effect, treatment difference and the corresponding 90% CI will be obtained by applying the same standardization procedure as above.

The response or remission at each assessment will be flagged out in the individual listing of MADRS scores.

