### **12.5.1 Efficacy and/or Pharmacodynamic endpoint(s)**

To assess the effect of MIJ821 on sustained response and remission, following secondary efficacy endpoints will be evaluated:

- Proportion of participants meeting response criteria ( $\geq 50\%$  reduction from baseline in MADRS total score) over time in the Core Period.
- Proportion of participants meeting criteria for sustained response ( $\geq 50\%$  reduction from baseline in MADRS total score sustained for a period of at least four weeks) in the Core Period
- Proportion of participants meeting remission criteria (MADRS total score of  $\leq 12$ ) over time in Core Period
- Proportion of participants meeting criteria for sustained remission (MADRS total score of  $\leq 12$  sustained for a period of at least four weeks) in the Core Period
- Proportion of participants meeting criteria for relapse over all randomized population over fixed period in the Extension Period
- Proportion of relapsing participants meeting response criteria or remission criteria after the first infusion of MIJ821 retreatment in the Extension Period

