1.2 Study objectives and endpoints

Table 1-1 Objectives and Related Endpoints

Objective(s)	Endpoint(s)
Primary objective(s)	Endpoint(s) for primary objective(s)

• Core: To investigate dose response relationship for 4 doses of MIJ821 vs. placebo	
• Change from baseline in MADRS total score at 24 hours after the start of the first infusion
Secondary objective(s)	Endpoint(s) for secondary objective(s)

• Core: To assess safety and tolerability of MIJ821	
• Number and severity of treatment-emergent adverse events (TEAEs), including AEs of special interest in Core Period

• Core and Extension: To assess the effect of MIJ821 on sustained response and remission	
• Proportion of participants meeting response criteria ($\geq 50\%$ reduction from baseline in MADRS total score) over time in Core Period.• Proportion of participants meeting criteria for sustained response ($\geq 50\%$ reduction from baseline in MADRS total score sustained for a period of at least four weeks) in Core Period• Proportion of participants meeting remission criteria (MADRS total score of ≤ 12) over time in Core Period• Proportion of participants meeting criteria for sustained remission (MADRS total score of ≤ 12 sustained for a period of at least four weeks) in Core Period• Proportion of participants meeting criteria for relapse over all randomized population over fixed period in Extension Period• Proportion of relapsing participants meeting response criteria or remission criteria after the first infusion of MIJ821 retreatment in Extension Period

• Core and Extension: To assess MIJ821 pharmacokinetics in plasma	
• PK parameters of MIJ821 in plasma after 1st infusion described by AUClast, Cmax, Tmax (parameters not limited) and after each infusion described by Cmax and Tmax

Objective(s)	Endpoint(s)

Objective(s)	Endpoint(s)

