2.1.3 Analysis sets

The Randomized Set (RAS) consists of all randomized participants. The descriptions of population will be based on RAS.

The Full Analysis Set (FAS) comprises all randomized participants who received at least one dose of randomized study treatment. Participants will be analyzed according to the treatment they have been assigned to during the randomization procedure. The primary efficacy analysis for data in Core Period will utilize this analysis set.

The Safety Set (SAF) includes all participants who received at least one dose of study treatment. Participants will be analyzed according to the treatment received. In case participants take the wrong treatment (different with the assigned treatment), the first treatment received will be used in analysis. Safety analysis for data in Core Period will be based on SAF.

The Extension Set (ENS) is defined to include all subjects who joined Extension Period. Data collected during follow-up period will be analyzed based on ENS, and grouped by the assigned treatment in Core Period. In case participants take the wrong treatment during Core, the first actual treatment taken will be used for the analysis of safety data only. The analysis of data collected during extension period (before and after re-treatment period) will be based on ENS.

The Retreatment Set (RTS) is defined as a subset of SAF including participants who received at least one dose for the retreatment of relapse. Participants will be analyzed according to the treatment received for the first injection during the Retreatment Period. The efficacy and safety endpoints pertinent to Retreatment Period (see [Table 2-1](#)) will be analyzed based on RTS.

PK Analysis Set (PKS) includes all participants who provided at least one evaluable PK concentration. Determined PK concentrations may be excluded from the PKS (per the scientific judgement of the PK scientist, e.g. non-plausible concentrations). All subjects within the PK analysis set will be included in the PK data analysis. PK samples from subjects treated with MJJ821 will be measured and PK samples from placebo treated subjects will not be measured.

[REDACTED]

[REDACTED]

[REDACTED]

[REDACTED]

[REDACTED]

[REDACTED]

[REDACTED]

[illegible]

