2.5.1 Secondary endpoints

To assess the effect of MIJ821 on sustained response and remission, following secondary efficacy endpoints will be evaluated:

- Proportion of participants meeting response criteria ($\geq 50\%$ reduction from baseline in MADRS total score) over time in the Core Period.
 - Participants who do not meet the criterion or discontinue Core Period prior to the time point due to any reason or with missing score (baseline and/or post baseline) will not be considered as "a responder" at that timepoint.
- Proportion of participants meeting criteria for sustained response ($\geq 50\%$ reduction from baseline in MADRS total score sustained for a period of at least four weeks) in the Core Period

- The sustained response ideally requires all scheduled assessments over four weeks achieving 50% reduction from baseline. However, if there is one or more missing assessment(s) between two responses, the response will be assumed to be sustained over missing assessment(s), unless other specified. For example, one participant observed a response at Day 1 4 hours, Day 29 -2 hours, however missed the assessment at 24 hours, Day 8, Day 15 and Day 22, this participant is still considered as meeting the sustained response. The missing due to study discontinuation will not be imputed. Participants who do not meet the criterion will not be considered as “a responder” at the timepoint.
- Proportion of participants meeting remission criteria (MADRS total score of ≤ 12) over time in Core Period
 - Participants who do not meet the criterion or discontinue prior to the time point due to any reason or with missing score (either at baseline or post baseline) will not be considered as “a remitter” at that timepoint.
- Proportion of participants meeting criteria for sustained remission (MADRS total score of ≤ 12 sustained for a period of at least four weeks) in the Core Period
 - The rule for sustained remission is the similar with sustained response. Participants who do not meet the criterion will not be considered as “a remitter” at the timepoint.
- Proportion of participants meeting criteria for relapse over fixed period in the Extension Period
 - The definition and criteria of relapse could be referred to protocol section 3.4. The relapse will be evaluated by investigator and reported in the CRF form “Relapse and re-treatment criteria”. Participants without relapse reported will not be counted.

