2.5.3 Handling of missing values/censoring/discontinuations

The handling of missing data has been described for each endpoint in [Section 2.5.1](#). The missing value due to discontinuation will not be imputed.

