2.11 Interim analysis

One unblinded analysis will be performed when all participants completed Day 57 (2 weeks follow-up visit after the End of Core visit on Day 43). Data from Core Period will be analyzed according to the plan herein. The optimal dose will be identified based on the dose-response relationship established by MCP-Mod, as well the sustained efficacy effect, safety profile and PK of each MIJ821 dose and regimen compared to placebo.

This unblinded interim analysis will be conducted by study team. The individual level data will maintain blinded to investigators and participants until final database lock.

3 Sample size calculation

With the randomization ratio of 2:1:2:2:2 for the biweekly dosing arms, the sample size of 27:14:27:27:27 for placebo, MIJ821 0.0048 mg/kg, MIJ821 0.016 mg/kg, 0.048 mg/kg and 0.16 mg/kg, will provide about 80% power to detect a dose-response signal [to reject the null hypothesis of a flat dose-response curve where all MIJ821 dose means are equal to the placebo mean] for the biweekly dosing arms in change from baseline in MADRS at 24 hour using MCP-Mod methodology at the one-sided $\alpha = 0.05$ level. Since MIJ821 0.0048 mg/kg is

potentially non-effective, the sample size for this arm is chosen to be 50% of other arms and is sufficient for establishing the dose-response curve.

The 6 candidates DR curves (2 Emax, 4 Sigmoid Emax) for power calculation are defined in [Section 2.4.2.](#) [REDACTED]

[REDACTED]

For the two single infusion arms of 0.048 mg/kg and 0.16 mg/kg, to maintain the same precision as for the biweekly dosing arm vs placebo, 27 participants per arm are needed. In total the study needs 177 patients. Assuming a 10% dropout rate, approximately 195 pts in total (15 pts for 0.0048 mg/kg and 30 pts for the remaining 6 treatment arms) will be randomized.

All treatment arms (including both regimen) will be included in the MCP-Mod for the primary analysis which will provide about 92% power to detect a dose-response signal in change from baseline in MADRS at 24 hour using MCP-Mod at the one-sided 0.05 level.

4 Change to protocol specified analyses

Not applicable.

5 Appendix

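### The relapse endpoint has three conflicting denominators, and its 1 to 12 month proportions appear to count early leavers as relapse-free; SAP Section 4 declares no change.

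*SAP*

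**What the plan says.** Three denominators appear for one secondary endpoint.

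- **All randomised.** Protocol 12.5.1 (and Table 2-1): "Proportion of participants meeting criteria for relapse over all randomized population over fixed period in the Extension Period". SAP Table 1-1 repeats this: "Proportion of participants meeting criteria for relapse over all randomized population over fixed period in Extension Period".
- **Extension Set.** SAP 2.5.1 drops the reference to all randomised participants, and the analysis-set bullet in SAP 2.5.2 reads "Proportion of participants meeting criteria for relapse over fixed period in the Extension Period will be based on ENS". SAP 2.1.3 defines the set: "The Extension Set (ENS) is defined to include all subjects who joined Extension Period". That includes Day 43 non-responders.
- **Day 43 responders and remitters.** Later in SAP 2.5.2, the proportions over 1, 2, 3, 6, 9 and 12 months "will be plotted for each treatment arm based on ENS for responders/remitters at EoC visit". The same subset is used for a Kaplan-Meier analysis of time to first relapse, with a 90% CI for the median and no stated censoring rule.

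On people with no recorded event, SAP 2.5.1 says "Participants without relapse reported will not be counted", and SAP 2.5.3 says "The missing value due to discontinuation will not be imputed".

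SAP Section 4, "Change to protocol specified analyses", lists none. The SAP document history logs the new Extension Set and the added Kaplan-Meier analysis, but no change of endpoint denominator.

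Protocol 3.3 follows participants who are neither responders nor remitters for 8 weeks, against up to 52 weeks for the others.

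**The concern.** Two programmers working from this text could produce different relapse tables, and neither could be called wrong. None of the three versions is safe to read across arms without further rules.

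- Day 43 response happens after randomisation and may depend on dose, so a comparison among responders is no longer randomised.
- Over all randomised, if only responders can contribute a relapse, an arm with few responders gets a low relapse rate for the wrong reason.
- Over all randomised or the Extension Set, non-responders followed for 8 weeks would count as relapse-free at 3 to 12 months unless a rule says otherwise.
- The landmark proportions are crude, so early leavers lower the figure.

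Durability of effect and the effect on relapse are stated purposes of the Extension (Protocol 1.2). Time to relapse is also reported at the interim analysis (SAP 2.1), which serves Phase 3 dose and regimen selection.

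**Working it through.** The documents give no response, relapse or Extension drop-out rates, so there is no plan figure for this endpoint to reproduce. From Protocol 12.8.1 come the arm sizes (30 in six arms, 15 at 0.0048 mg/kg: 6 × 30 + 15 = 195) and a 10% drop-out allowance made for sample size. Every other rate below is my assumption.

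**1. Drop-out counted as relapse-free.** Take independent exponential relapse and drop-out over one year, with l = −ln(1 − q) for true relapse q and k = −ln(1 − d) for drop-out d. The crude proportion is l/(l + k) × [1 − exp(−(l + k))].

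- q = 50%, d = 10%: l = 0.693, k = 0.105; 0.868 × (1 − 0.5 × 0.9) = 0.868 × 0.55 = 47.7%.
- q = 50%, d = 20%: k = 0.223; 0.756 × 0.60 = 45.4%.
- q = 50%, d = 30% or 40%: 42.9% or 40.3%.

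Kaplan-Meier with independent censoring estimates the 50%. With equal 10% drop-out, a true 50% v 40% (placebo v active) becomes 47.7% v 38.1%, in the same order. Reversal needs far more placebo drop-out: about 30% v 10% when true relapse is 50% v 45%, and about 50% v 10% when it is 50% v 40%.

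**2. All randomised, counting only responders' relapses.** The proportion is R × q, with R the Day 43 response rate and q relapse among responders. The active arm looks worse when q(active)/q(placebo) exceeds R(placebo)/R(active).

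| R, placebo v active | q, placebo v active | R × q, placebo v active | Active looks worse? |
|---|---|---|---|
| 40% v 60% | 50% v 40% | 20% v 24% | yes |
| 30% v 60% | 50% v 35% | 15% v 21% | yes |
| 40% v 60% | 50% v 25% | 20% v 15% | no |
| 40% v 50% | 50% v 35% | 20% v 17.5% | no |

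With 90% entering the Extension, the first row over the Extension Set is 0.20/0.90 = 22.2% v 0.24/0.90 = 26.7%, in the same direction. In that row, responders still relapse-free over all randomised are 0.40 × 0.50 = 20% v 0.60 × 0.60 = 36%.

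**3. Responders only.** Suppose those who would respond on either treatment relapse at 40% on placebo and 32% on drug, and those who respond only on drug relapse at x. Active-arm relapse among responders is [R(placebo) × 0.32 + (R(active) − R(placebo)) × x]/R(active).

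- Response 30% v 60%, x = 60%: (0.096 + 0.180)/0.60 = 46%, against 40% on placebo, although the drug lowers relapse in the first group.
- Same response, x = 40%: 36%, so no reversal. Break-even is x = 48%.
- Break-even is 56% at response 40% v 60%, and 72% at 40% v 50%.

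**4. Dependence on the non-responder rule.** I simulated identical individual relapse hazards in both arms: vulnerability u standard normal, six-month hazard exp(−1.2 + 0.6u), responders the lowest 60% (drug) or 40% (placebo) of u plus normal noise with SD 0.8. Relapse among responders is about 22% v 19% (drug v placebo). Over all randomised, counting responders only, it is 12.9% v 7.5%. If everyone's relapse counted, it would be about 28.6% in both arms. The apparent excess in the all-randomised figure comes from the counting rule, which the SAP does not state.

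**The case against.** The strongest reply is that this is a descriptive endpoint. SAP 2.5.2 tests no hypothesis on the secondary efficacy endpoints, and relapse is not among the four endpoints for which it plans treatment differences against placebo. Response and sustained response are already analysed on the FAS. A Kaplan-Meier analysis sits beside the crude proportions and would normally censor early leavers. This stands: no type I error is affected, and drop-out is partly handled.

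Several stronger readings are tempting, and the documents do not support them.

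- *A non-responder cannot relapse.* Protocol 3.3 withholds retreatment from non-responders should they relapse, so it contemplates the event. SAP Table 5-2 also lists absence of relapse and absence of response as separate exclusions. The gap is an unstated rule, not a proven bias.
- *Drop-out makes the drug look worse.* Equal drop-out does not reverse the arms. That early leavers count as relapse-free is itself an inference from an unclear sentence, and it concerns the crude proportions only.
- *The result will point the wrong way.* Reversal is possible under ordinary assumed rates, but not shown. With 18 v 12 responders, the 22% v 19% gap has a standard error of about 15 points, so it would not be visible in this trial.
- *Dose selection rests on the crude proportions.* SAP 2.1 brings time to relapse into the interim analysis, not the landmark proportions. Protocol 4.4 bases the choice on Core Period data, though not exclusively, and neither interim analysis section names relapse.

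What survives is the undeclared conflict of denominators, the downward bias of the crude proportions on their natural reading, and the absence of rules for non-responders and for censoring.

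**Conclusion.** The concern holds as a should-fix. The three denominators and the empty Section 4 can be read directly from the documents. The understatement of relapse depends on the natural reading of SAP 2.5.1 and 2.5.3. Under independent exponential relapse and drop-out it is about 2 percentage points at 10% yearly drop-out and about 5 at 20%, for a true 50%. Misranking of an effective dose can occur under either the responder-only or the all-randomised version, but it depends on assumed response and relapse rates. For the all-randomised version it also depends on counting responders' relapses only. The consequence is a possible misreading of durability across arms and regimens, not a false-positive test.

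**What to change.** 1. Bring SAP Table 1-1, 2.5.1 and 2.5.2 to one declared denominator. State whether a Day 43 non-responder's relapse counts and how the 8-week follow-up enters the later landmarks. State how relapses on or after week 38 are counted, since Protocol 3.3 then sends the participant to the End of Study visit. Record the departure from the protocol in SAP Section 4.
2. Replace the crude proportions at 1, 2, 3, 6, 9 and 12 months by one minus the Kaplan-Meier estimate at the same months, with 90% CI, censoring at the last relapse assessment.
3. Label the responder-only Kaplan-Meier curves and landmarks as descriptive and non-randomised.
4. Optionally add a supplementary descriptive table over the FAS by Core arm: the proportion in response or remission at Day 43 and still relapse-free at each landmark. This keeps the randomised groups, but it mixes response with relapse. It is partly a matter of preference and should not displace the declared endpoint.

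The cost is SAP wording and a few tables. No new data are needed.

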### 6.1.3 Treatment arms/group

This study consists of seven treatment arms, participants will be randomized in a 2:1:2:2:2:2:2 ratio on Day 1 to the following treatment arms on the top of the ongoing SoC:

- Placebo, one infusion every other week on Day 1, Day 15 and Day 29 of treatment (Core Period only)
- MIJ821 fixed dose of 0.0048 mg/kg, one infusion every other week on Day 1, Day 15 and Day 29 of treatment/ relapse retreatment
- MIJ821 fixed dose of 0.016 mg/kg, one infusion every other week on Day 1, Day 15 and Day 29 of treatment/ relapse retreatment
- MIJ821 fixed dose of 0.048 mg/kg, one infusion every other week on Day 1, Day 15 and Day 29 of treatment/ relapse retreatment
- MIJ821 fixed dose of 0.16 mg/kg, one infusion every other week on Day 1, Day 15 and Day 29 of treatment/ relapse retreatment
- Single administration MIJ821 0.048 mg/kg, one infusion on Day 1, followed by placebo infusions every other week on Day 15 and Day 29 of treatment / relapse retreatment
- Single administration MIJ821 0.16 mg/kg, one infusion on Day 1, followed by Placebo infusions every other week on Day 15 and Day 29 of treatment / relapse retreatment

In all treatment arms, investigational treatment will be administered by intravenous infusion every other week, 3 infusions in total during the placebo-controlled double-blind Core, 6-week period of the study.

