2.4.1 Primary endpoint(s)/estimand(s)

The primary estimand, defined below, quantifies the treatment effect of MIJ821 at 24 hours post first dose administration while accounting for intercurrent events with potential confounding effects and intercurrent events leading to study discontinuation prior to the 24 hours assessment.

Population: Participants with MDD who have suicidal ideation with intent. All participants included in FAS will be counted.

Variable: Change from baseline in MADRS total score at 24 hours post first dose administration (see definition in [Section 2.4.1.1](#))

Treatment:

There are 6 active MIJ821 dose arms and 1 placebo arm as described in [Section 1.1](#).

- Placebo every other week
- MIJ821 0.0048 mg/kg every other week
- MIJ821 0.016 mg/kg every other week
- MIJ821 0.048 mg/kg every other week

- MIJ821 0.16 mg/kg every other week
- MIJ821 0.048 mg/kg single infusion with two subsequent placebo dosages given every other week
- MIJ821 0.16 mg/kg single infusion with two subsequent placebo dosages given every other week

Since the MADRS total score at 24 hours will be evaluated post the single first injection, treatment arms with different regimens will be grouped into one arm, which turns out to be 4 pooled dose arms and 1 placebo arm during the analysis of this primary estimand:

- Placebo every other week
- MIJ821 0.0048 mg/kg
- MIJ821 0.016 mg/kg
- MIJ821 0.048 mg/kg
- MIJ821 0.16 mg/kg

on top of ongoing pharmacological antidepressant SoC treatment. Dosage titration or adjustments of standard-of-care antidepressant treatment occurred during the first 2 weeks of double-blind treatment are allowed, if needed, with dosages maintained thereafter during the Core Period.

Intercurrent Events (not limited to):

Intercurrent events with potential confounding effect to MADRS assessment at 24-hour:

- Intake or changes in concomitant medications/therapies other than SoC which have potential confounding effects
- Intake of prohibited medications with potential effect
- Intake of rescue medications
- Pandemic related intercurrent events

Participants who took prohibited medications/prohibited therapy treatment or concomitant medications with potential confounding effect and rescue medications will continue to stay in the study. The confounding effect from these medications or therapies will be identified by the approach defined in [Section 2.3.2](#).

Intercurrent events leading to study discontinuation prior to the 24 hour assessment:

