2.4.6 Supportive analyses

MADRS score over visit

Based on FAS, the summary statistics for absolute values and change from baseline of MADRS score by treatment arm (6 dose arms and 1 placebo arm) and analysis visit in Core Period and 2 weeks follow-up in Extension Period, will be provided for the original measurements (i.e. the raw data prior to missing data handling using multiple imputation) of the primary endpoint.

The change from baseline in MADRS score (original measurements) from above visits will also be analyzed using the mixed-effects model for repeated measures (MMRM). This model will include the fixed, categorical effects of treatment, region, time (all analysis visits), and

treatment*time interaction, as well as the continuous, fixed covariates of baseline MADRS score, and baseline MADRS score*time interaction. An unstructured variance-covariance structure will be used to model the within-subject errors. The Kenward-Roger method will be used to adjust the estimated covariance of the mean difference and the degrees of freedom. If the analysis with unstructured covariance structure fails to converge, the compound symmetry will be tested. Model estimated means and their differences of each MIJ821 doses vs. placebo, will be obtained at each timepoint, along with the 90% CI for the difference. Model estimated treatment means in change from baseline in MADRS score (\pm SE) will be plotted over time/visit.

For participants who take retreatment for relapse, the summary statistics for absolute values of MADRS score and change from the baseline of retreatment will be provided in the similar manner, based on RTS. No inferential test analyses will be performed for the retreatment due to limited data.

The individual MADRS scores will be presented in listing.

Individual Item Analyses

Descriptive statistics (n, median, minimum and maximum) will be provided for MADRS item 10 ("Suicidal thoughts") score at baseline and the changes from baseline value at each visit. The treatment difference will be estimated for item 10 using the Hodges-Lehmann estimate, which is the median of all possible paired differences for the change from baseline for individual item. Hodges-Lehmann estimates and the corresponding 90% CI for the treatment differences will be provided for each timepoint.

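### Until the Day 15 infusion the two regimens at 0.048 mg/kg, and the two at 0.16 mg/kg, are the same treatment, but the by-visit response and remission model shows no pooled same-dose contrast

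*SAP*

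**What the plan says.** Protocol 6.1.3 defines the lower single-infusion arm as "Single administration MIJ821 0.048 mg/kg, one infusion on Day 1, followed by placebo infusions every other week on Day 15 and Day 29", and defines the 0.16 mg/kg arm in the same way. The matching biweekly arms receive active drug on Days 1, 15 and 29. Within each dose, the two arms are therefore treated alike until the second infusion.

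The SAP uses this in two places. For the primary estimand at 24 hours (SAP 2.4.1), "treatment arms with different regimens will be grouped into one arm", leaving four doses and placebo. For PK after the first infusion (SAP 2.7), parameters are summarised by dose with the regimens combined, as well as by regimen.

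The by-visit efficacy analyses are set up differently:

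- **Response and remission by visit (SAP 2.5.2).** The "repeated logistic regression model will be established with the fixed, categorical effects of treatment (6 dose arms and 1 placebo arm"), with time and a treatment-by-time interaction. That is seven treatment levels at every visit. The text directly after this sentence is redacted.
- **MADRS by visit (SAP 2.4.6).** Summary statistics are given "by treatment arm (6 dose arms and 1 placebo arm) and analysis visit in Core Period". The MMRM that follows names a treatment effect without its number of levels and reports each dose against placebo with a 90% CI. The item 10 Hodges-Lehmann estimates do not state their grouping.
- **Default (SAP 2.1).** Output is by treatment arm unless otherwise specified. Pooling is referred to Section 2.4.1, and further details of arm handling to the table shells.

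SAP 2.5.2 also states that no hypothesis is tested for the secondary efficacy endpoints.

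**The concern.** The reason for pooling at 24 hours is that only one infusion has been given. That reason applies equally at 4 hours, Day 8 and Day 15 pre-dose. A model that keeps the same-dose arms apart at these visits returns two estimates of one treatment effect, each based on half of the active participants available at that dose. At 24 hours the two response estimates would stand beside a pooled primary estimate.

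Protocol 4.2 includes the single-infusion arms, with weekly MADRS measurements, to establish how long the effect lasts. Day 8 and Day 15 pre-dose are the visits at which everyone given that dose informs the duration of a single infusion. Because no test is made, the width of the interval is what these analyses contribute to dose selection. If the pooled contrast is not pre-specified, someone has to choose after unblinding which same-dose estimate to cite.

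**Working it through.** **Inputs (SAP Section 3).** Evaluable numbers are "the sample size of 27:14:27:27:27 for placebo, MIJ821 0.0048 mg/kg, MIJ821 0.016 mg/kg, 0.048 mg/kg and 0.16 mg/kg". For the single-infusion arms, "to maintain the same precision as for the biweekly dosing arm vs placebo, 27 participants per arm are needed". The section continues: "In total the study needs 177 patients" and "Assuming a 10% dropout rate, approximately 195 pts in total (15 pts for 0.0048 mg/kg and 30 pts for the remaining 6 treatment arms").

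**The plan's own figures.**

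- Evaluable: 6 × 27 + 14 = 176, against 177 stated.
- Randomised: 15 + 6 × 30 = 195, as stated. Multiplying, 177 × 1.10 = 194.7, which rounds to 195; dividing, 177 / 0.90 = 196.7, which rounds up to 197. The figures reproduce to within rounding.
- Power: about 80% with the biweekly arms only and about 92% with all arms. Effect, SD and curve parameters are redacted, so neither can be recomputed. As a plausibility check, three assumed sets of two Emax and four sigmoid Emax curves were scaled to give 80% (average or minimum over the six curves) with 27:14:27:27:27. With 27:14:27:54:54 the same criterion gave 85% to 91%, and single curves 81.1% to 97.5%. The stated gain is plausible.

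**Which visits qualify.** Protocol Section 8 allows ±3 days, so an in-window second infusion falls on Day 12 or later. SAP Table 2-2 maps Days 3 to 11 to Day 8. The MADRS assessments at 4 hours, 24 hours, Day 8 and Day 15 pre-dose all precede the second infusion.

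**Mean MADRS change, one dose against placebo, common SD σ.**

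- Separate: (1/27 + 1/27)σ² = 0.0741σ².
- Pooled: (1/27 + 1/54)σ² = 0.0556σ².
- Information kept by separate arms: 0.0556 / 0.0741 = 0.75, a loss of 25%.
- Gain from pooling: 0.0741 / 0.0556 = 1.333, or 33%.
- 90% CI half-width: 1.645 × √0.0741 = 0.448 SD separate; 1.645 × √0.0556 = 0.388 SD pooled. The ratio is √0.75 = 0.866, so the interval is 13% narrower. The ratios are the same with 30 per arm.

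**An averaged contrast recovers this.** In the linear seven-arm model, the equal-weight average of the two same-dose means, minus placebo, has variance ¼(1/27 + 1/27)σ² + (1/27)σ² = (1/54 + 1/27)σ². This is the pooled value, apart from covariate adjustment and missing data.

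**Response or remission, difference in proportions.** With V = p(1−p), the loss is 1 − (Vp/27 + Va/54) / (Vp/27 + Va/27) = 0.5 × Va / (Vp + Va), where p is placebo and a is active. The documents give no rates. For assumed placebo rates of 10% to 40% and higher active rates of 20% to 70%:

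| Assumed placebo rate | Assumed active rate | 90% CI half-width, separate | 90% CI half-width, pooled | Loss |
|---|---|---|---|---|
| 40% | 70% | 0.212 | 0.186 | 0.5 × 0.21/0.45 = 23% |
| 30% | 50% | 0.215 | 0.183 | 0.5 × 0.25/0.46 = 27% |
| 10% | 50% | 0.185 | 0.147 | 0.5 × 0.25/0.34 = 37% |

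The first and last rows are the extremes of the grid.

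**The case against.** The strongest reply has four parts.

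- **Redaction.** The passage after the logistic model is blacked out. The later reference to the same standardisation procedure shows that the hidden text deals with how arm effects and differences are formed. A pooled contrast could be there or in the table shells. This stands: one can say only that none is visible.
- **Regimen-level output is deliberate.** The interim analysis judges each dose and regimen, and the duration of a single infusion needs a trajectory by arm. This stands as a reason to keep the seven arms. It is no reason to omit an extra contrast.
- **Low stakes.** The MCP-Mod analysis at 24 hours is already pooled. The secondary models are fitted only if data warrant and test nothing. No data are discarded, since the two arm estimates can be averaged. This stands and limits the severity.
- **Pooling would not make the 24-hour MADRS estimates agree.** The MMRM uses unimputed measurements, while the primary analysis excludes values after some intercurrent events and uses multiple imputation. This also stands. The case for the contrast is precision, not agreement.

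A reader might go further and infer that every secondary and supportive model has this fault. The documents do not support that. Sustained response and remission last at least four weeks and so cross Day 15, and relapse is assessed in the Extension Period; separate regimens are right there. The seven-arm wording in SAP 2.4.6 belongs to the summary statistics, so the MMRM and item 10 groupings are inferred. A reader might likewise object to adverse events being split by regimen. That rests only on the by-arm default in SAP 2.1; the adverse event sections describe no separate first-infusion incidence table.

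**Conclusion.** The point holds for response and remission by visit, where seven levels are stated, and probably for the MADRS MMRM and item 10, where they are implied. At 4 hours, 24 hours, Day 8 and Day 15 pre-dose, each 0.048 or 0.16 mg/kg comparison of mean MADRS change with placebo carries about 25% less information than a pooled contrast. This assumes equal variances and 27 or 30 per arm. For response-rate differences the loss is about 23% to 37%, under assumed rates.

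A reader might put the loss at one third. That figure is the gain from pooling relative to separate arms, or the share of participants outside one contrast (27 of 81). Measured against the pooled contrast, the loss for a mean difference is one quarter.

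This is a modest loss of efficiency with an almost free remedy. It introduces no bias and leaves the primary analysis untouched. It falls away if the redacted text already specifies a pooled contrast.

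**What to change.** In SAP 2.5.2 and 2.4.6, state the treatment levels of each model and keep the seven-arm results. Unless the redacted text already does so, pre-specify one additional contrast for 0.048 mg/kg and one for 0.16 mg/kg: the equal-weight average of the two same-dose arms against placebo, at assessments before the second infusion. In the logistic model, average the standardised proportions. For item 10, which has no model, pool the two arms directly. Define eligibility by the actual time of the second infusion, so that visit remapping cannot bring in post-infusion data. Keep seven arms after the Day 15 infusion and for sustained response and remission.

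Optionally, add one table of adverse events and AESIs by pooled dose, limited to onset before the second infusion. If all those randomised are dosed, its denominator rises from 30 to 60 at these two doses.

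The cost is a few contrast statements and, if wanted, one table. No new data are needed. The reports gain a further set of estimates, which should be labelled as single-infusion effects by dose.
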